Number of Subjects/Patients	Up to 800 subjects will be recruited, comprising up to 400 SA and 400 WB, each including patients, recovered and uninfected subjects.
Trial Design	Cross sectional with longitudinal component. Samples of SWMF, and blood and a detailed mouth examination on all participants. Lymphocyte phenotypes in blood and SWMF compared, cytokines and serum and secretory antibodies to SARS-CoV2 antigens. DNA extraction from SWMF for meta-analysis of oral microbiome, and metabolome and proteome analysis
Endpoints	
 1. Patients recruited 2. Samples collected and processed 3. Generation of raw data
Main Inclusion Criteria	
 • South Asian* and White British persons and those diagnosed with current or past symptomatic or asymptomatic SARS-CoV2 infection, or uninfected. • Aged 18 or over. • Able to understand and consent. • For in patient groups: Confirmed COVID-19 positivity, symptoms and symptom onset within the past 21 days;
Statistical Methodology and Analysis	
A total sample size of up to 800 participants, up to 400 of which will provide samples at three further time points. Between 30 and 50 values per parameter would be needed to demonstrate statistical differences on a cross sectional basis and 30-40 per parameter on a sequential basis.
 
The microbiome, clinical data and immunome data will be associated using Spearman correlations. A Mann–Whitney U-test will be used to determine the median differences of continuous clinical variables. For more than two groups, the Kruskal–Wallis test with post-hoc Dunn test will be used.

*South Asian defined as those of Indian sub-continent origin.

There is no device or product used in this study

Glossary of Terms and Abbreviations

AE Adverse Event

AR	Adverse Reaction
ASR	Annual Safety Report
CA	Competent Authority
CI	Chief Investigator
CRF	Case Report Form
CRO	Contract Research Organisation
DMC	Data Monitoring Committee
EC	European Commission
GAfREC	Governance Arrangements for NHS Research Ethics Committees
GSTT	Guys & St Thomas Hospital
ICF	Informed Consent Form
ISRCTN	International Standard Randomised Controlled Trial Number
KCH	King's College Hospital
KCL	King's College London
MA	Marketing Authorisation
MS	Member State
Main REC	Main Research Ethics Committee
NHS R&D	National Health Service Research & Development
PI	Principal Investigator
QA	Quality Assurance
QC	Quality Control

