2.1. Trial Objectives

- Primary Objective

The key aim of this research in South Asian populations and White British populations, is to find out whether differences in COVID-19 morbidity and mortality in similar populations in the UK might be related to mucosal immunity expressed in the mouth and to the oral microbiome (the total bacteria, fungi and viruses living in the mouth). This will be achieved by determining

whether in the mouth there are differences between the participant groups of mucosal natural immunity (innate immunity), immune responses to SARS-COV2 antigens (adaptive immunity), or the oral microbiome

- Secondary Objectives

1. To determine whether differences in mucosal immunity or differences in the oral microbiome correlate with susceptibility to COVID-19 infection, or to progression and recovery from the disease.

2. To determine whether the presence of pre-existing oral disease is related to susceptibility to SARS-CoV2 infection, to severity of COVID-19 disease or relates to the nature of mucosal immunity and to the composition and activity of the oral microbiome

- Primary End Point

- Collection, processing and analysis of samples. Statistically significant quantitative differences in measured mucosal innate immune factors, mucosal adaptive immune factors and/or in the oral microbiome in relation to 1) a comparison between South Asian and White British populations in the UK 2) the degree of severity of COVID in South Asian and White British participants in the UK

- Secondary End point

- Generation of raw data.
- *a comparison between South Asian populations in the UK and in Chennai, India.

**Note: This is the UK part of an international research collaboration between the UK (funded by the MRC) and India (funded by the DBT) with research being carried out separately but in parallel in the two Countries and generating results which will be directly compared.*

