2.4 Trial Statistics

Statistical advice indicates that with expected variation in both immunological and microbiome parameters, between 30 and 50 values per parameter would be optimal to demonstrate statistical differences on a cross sectional basis (more than 21 for immunological samples, more than 30 for microbiome samples) and that 30-40 per parameter would be optimal on a sequential basis. We

have therefore aimed for a minimum of 50 and a maximum of 100 participants for the cross sectional comparison, and between 30 and 50 participants on a longitudinal basis. Groups of 100 for the cross-sectional part of the study and 50 for the sequential also allow for the unexpected withdrawal of participants and leave sufficient numbers of samples for statistical analysis.

The microbiome, clinical data and immunome data will be associated using Spearman correlations. A Mann–Whitney U-test will be used to determine the median differences of continuous clinical variables. For more than two groups, the Kruskal–Wallis test with post-hoc Dunn test will be used. The association between the prototype prevalence, immunome and clinical data will be modelled with single (univariate) or multiple (multivariate) dependent variables (clinical & immunome metadata features) and will be performed using multinomial or binomial logistic regression.

Standard pipelines and statistical methods already in use within the group will be used for oral metagenome data. The data will be initially quality controlled and trimmed. Human contaminant sequences will be removed from reads by mapping against a human reference genome using Bowtie2. Scaffolds will be assembled from filtered reads using SPAdes. SAMtools will be applied to generate statistics for each filtered scaffold. The scaffolds will be merged to one scaffold file and bacterial genes from the file will be identified using Prodigal. The genes will be clustered and redundant genes will be removed using CD-HIT. Next all the unmapped reads will be mapped to the list of assembled genes and using METEOR software suite the gene counts will be generated for each sample and according to the depth of the sample sequence data, the count table will be downsized. Then the updated count table will be normalized to the gene length and converted to a frequency matrix, which we call the Gene Abundance Matrix.

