The gene richness analysis will be done based on the updated count matrix to obtain the diversity of the samples at the gene level. A Wilcoxon test follow by Benjamini-Hochberg multiple testing correction will be used to obtain the significant changes between the cohorts. Next, we will map each sample to our already generated 1,942 oral Metagenomic Species Pangenomes (MSP), as an updated format for the metagenome species. The relative abundance of an MSP will be calculated using the mean abundance of its 100 ‘marker’ genes. To contrast the species abundance in different cohorts, we will perform Benjamini-Hochberg multiple testing correction of a Wilcoxon test. Functional analysis will also be performed using the PFAM and KEGG databases. Antimicrobial resistance analysis will be performed by searching reads using the CARD (Comprehensive Antimicrobial Resistance Database) database. In addition, “ortotyping” will be performed using the microbial information on the genus-level abundance with a Hellinger transformation with a Dirichlet multinomial mixtures (DMM) approach to cluster individual samples to distinct groups based on their microbiome composition, and a Fisher’s exact test will be used to identify the prevalent ortotype.

3. Sample Size, Selection and Withdrawal of Subjects

The success of the national vaccination programme has necessitated casting the recruitment net more widely than originally anticipated. Sample size is discussed in 2.4

Uninfected (vaccinated or unvaccinated) will be identified by advertising within KCL and GSTT sites, and at PIC sites, via social media and by recruitment at vaccination centres at GSTT or

testing centres at KCL/GSTT. Patients admitted to wards for non-COVID reasons and found to be SARS-CoV2 negative will be invited to participate. Uninfected (vaccinated) will be identified by recruitment at vaccination centres and by advertising within KCL and GSTT and PIC sites. Uninfected participants will be further defined as those who do not show antibodies to nuclear capsid protein antigens. The presence of such antibodies would indicate exposure to SARS-CoV2 rather than immunisation, and would be classified as asymptomatic if no history of symptoms.

All will be given the Patient Information Leaflet (PIL) about the study and access to the study website (<https://www.kcl.ac.uk/research/mimsa>)

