Blood and SWMF pellet T cell phenotyping will be performed by flow cytometry (BD FACSLyric) using monoclonal antibodies (BD Biosciences) to T cell markers. Pan T cells – CD3; Helper T cells – CD4; CD4 T cell activation marker – CD25; Cytotoxic T cells – CD8; CD8 T cell activation marker – CD38; NK cells – CD56 and HLA-DR; Th17 and Th22 cells – CCR4, CCR10; Tfh cells - ICOS; Tregs – Foxp3; T cell exhaustion marker – PD-1; effector and memory T cells – CD45RA and CD45RO/CCR7; mucosal homing marker – CD69; airway homing marker – integrin β 1 and β 7. T cell phenotypes will be reported as percentages of the total T cells. Cells will be stained with the defined cocktail of antibodies for 15 minutes at room temperature in the dark; fixed and permeabilised; and then stained with intracellular antibodies (as appropriate) for 15 minutes; washed and analysed by flow cytometry.

For SWMF analysis, the samples will be gently centrifuged and a portion of the pellet resuspended in buffered saline, and incubated with the fluoresceinated antibodies before passing through an analyser.

Cytokine profiles will be analysed and quantified using the CBA kits (BD Biosciences) as per the manufacturer's instructions. Cytokines include IL-2, IL-4, IL-6, TNF- α , IL-1 β , IFN- γ , IL-17, IL-22, IL-23, IL-8, IL-12p70, TGF- β , IP-10, MIG, MCP-1, CCL-20. CBAs will be analysed by flow cytometry (BD FACSLyric). Total IgG will be detected in the serum/plasma and SWMF supernatant samples by ELISA as per the manufacturer's instructions.

All of the techniques have been established, used and validated in the CHMI laboratories.

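### The primary end point is statistical significance in any of three open domains with no named measure; at 5% per test, chance alone would satisfy it more often than not

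*Protocol*

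**What the plan says.** The primary end point in Protocol section 2.1 has two parts. The first is that samples are collected, processed and analysed. The second is "Statistically significant quantitative differences in measured mucosal innate immune factors, mucosal adaptive immune factors and/or in the oral microbiome". This second part applies to two contrasts: "a comparison between South Asian and White British populations in the UK" and "the degree of severity of COVID in South Asian and White British participants in the UK". No single marker, score, significance level or hierarchy is given.

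Section 5.1 sets out what is measured. The list beginning "Cytokines include IL-2, IL-4, IL-6" has 16 cytokines and chemokines. Blood and SWMF cells are phenotyped by flow cytometry, and "T cell phenotypes will be reported as percentages of the total T cells". Antibody is assayed against three peptides and capsid antigen, and total IgG is measured as well.

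The tests are in sections 2.4 and 5.5. Immune markers are compared by Mann-Whitney, or by Kruskal-Wallis with Dunn's test for more than two groups (section 5.5 also mentions Anova). For gene richness, "A Wilcoxon test follow by Benjamini-Hochberg multiple testing correction will be used to obtain the significant changes between the cohorts", and the same correction is stated for species abundance. Separately, "The microbiome, clinical data and immunome data will be associated using Spearman correlations".

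The synopsis gives a different list of end points: recruitment, "Samples collected and processed", and raw data generated. In section 2.1 the raw data are a secondary end point.

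**The concern.** An end point should be a quantity measured on participants, and significance is a verdict on such a quantity. Here the verdict is itself the end point, and the and/or lets a result in one domain, for one contrast, count. With dozens of immune read-outs and no stated adjustment across them, the wording would probably be satisfied even if mucosal immunity differed neither by ethnicity nor by severity.

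This matters because the Protocol intends more than description. The synopsis says that the study is not a pilot. The Introduction aims at diagnostic and prognostic utility and at biomarkers that allow earlier treatment, and section 5.1 looks for therapeutic targets. Such claims need an end point that can fail.

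**Working it through.** **The plan's own figure.** Section 2.4 asks for 30 to 50 values per parameter. It gives no effect size, standard deviation, significance level or power, so the figure cannot be reproduced. Assuming two-sided 0.05 and 80% power, the detectable standardised difference is (1.960 + 0.842) × √(2/n): 0.72 at n = 30 per group, 0.56 at n = 50 and 0.40 at n = 100. This neither confirms nor refutes the figure.

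**Number of immune read-outs (section 5.1).**
- Cytokines and chemokines: 16.
- Cell phenotypes, leaving out CD3 as the denominator: 12 as labelled. Splitting Th17/Th22, effector/memory and the two integrins gives 15.
- Antibody: 3 peptides + capsid + total IgG = 5.
- Total: 16 + 12 + 5 = 33, or 16 + 15 + 5 = 36.

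**Number of tests at baseline.** With one test per marker per contrast there are 33 × 2 = 66 tests, or 36 × 2 = 72. If severity is tested within each ethnic group, there are 33 × 3 = 99.

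**Chance of at least one significant marker when nothing differs**, at an assumed 0.05 per test. For independent tests it is 1 − 0.95^m:
- 16 cytokines, one contrast: 1 − 0.95^16 = 56%.
- 33 markers, one contrast: 1 − 0.95^33 = 82%.
- 66 tests: 1 − 0.95^66 = 96.6%, with 66 × 0.05 = 3.3 false positives expected.
- 72 tests: 97.5%.
- 99 tests: 99.4%.

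A simulation with the rank tests themselves (Mann-Whitney for ethnicity, Kruskal-Wallis over four groups, 33 independent markers, 300 runs) gave 95%.

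**Allowing for correlation.** Markers from one sample are correlated. Normal test statistics were simulated 20,000 times in blocks of 16, 12 and 5, with correlation within blocks, none between them, and independent contrasts.

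| Correlation | 2 contrasts | 3 contrasts |
|---|---|---|
| 0.3 within block | 94% | 98% |
| 0.5 within block | 88% | 96% |
| 0.7 within block | 77% | 89% |
| 0.7 across all 33 markers | 58% | 72% |

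These figures are for baseline only. Testing at four time points, with an assumed correlation of 0.5 over time, brings the block-correlated cases to 99% or more. That is an illustration, since Table 1 does not sample every group at every time.

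**What the stated corrections cover.** Dunn's test deals with pairs of groups within one marker and does nothing about the number of markers. Benjamini-Hochberg is attached to two metagenomic analyses. No control is stated across the three domains.

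**The case against.** The strongest objection is that the significance level and the correction across laboratory markers are often left to a statistical analysis plan, and one may exist. That stands as far as it goes: the missing correction alone is not the finding. But the definition of the primary end point belongs to the Protocol, and the Protocol fixes it as significance over an open set. A later correction would lower the error rate, but it would still not say which quantity is primary.

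It can also be said that the study is observational, that and/or may merely list the domains to be compared, and that section 2.4 speaks of values per parameter, which suggests marker-by-marker reporting. This is fair. The Protocol nowhere says that one p-value below 0.05 meets the end point. That reading follows naturally from the wording but is not a stated rule, and the 0.05 is an assumption.

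A reader might infer two stronger points, and the documents support neither:
- **That a positive result is close to certain under the null.** This needs nearly independent markers. With correlation the baseline figure falls to 77–94%, and to 58% in the most correlated case examined.
- **That the correlation analysis would yield about 3,500 false associations** (1,942 species × 36 markers × 0.05 = 3,496). The primary end point concerns differences between groups, not correlations. The 1,942 is the size of a reference catalogue, not a count of species detected here. Section 5.5 limits the comparison with the microbiome to key immunological parameters.

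**Conclusion.** The point holds. Beyond sample collection and analysis, the primary end point is statistical significance somewhere in three open domains and two contrasts, with no named measure. Under the stated tests, the chance of at least one significant immune marker at baseline when nothing differs is about 97% with independent markers, 77–94% with within-block correlation of 0.7 to 0.3, and 58% with a common correlation of 0.7. Even the lowest figure is more than ten times 5%.

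The result rests on an assumed two-sided 0.05 per test, a count of 33 read-outs and one test per marker per contrast. The count matters little (96.6% for 66 tests, 97.5% for 72); the correlation matters much more. A positive primary result would thus be weak evidence that mucosal immunity differs by ethnicity or severity. The mismatch between the synopsis and section 2.1 is a smaller, separate fault in the same definition.

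**What to change.** Restate the primary end point in section 2.1 as measured between-group differences at baseline, with 95% confidence intervals, in three declared families. Assign every SWMF immune and microbiome read-out to exactly one of them:
- innate: cytokines and NK cells;
- adaptive: T-cell phenotypes, antigen-specific antibody and total IgG;
- oral microbiome.

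Within each family, apply Benjamini-Hochberg (already in the plan for the metagenome) or Holm across both contrasts. Divide the 5% over the three families and claim the primary objective only for families that pass. If the families are independent and nothing differs, the chance of any false claim is then 1 − (1 − 0.05/3)^3 = 4.9%. Testing each family and contrast at 5% without dividing would leave 1 − 0.95^6 = 26%. Holm also limits false claims about single markers when some differences are real; Benjamini-Hochberg then limits only their expected proportion.

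Label the Spearman associations exploratory. Make the synopsis and section 2.1 list the same end points and give raw-data generation one status.

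The change is to wording and analysis, with no new samples or participants. The cost is fewer nominally significant markers and a larger detectable difference. As an outer bound, Bonferroni over 66 tests (0.05/66 = 0.00076) at 80% power raises the detectable standardised difference from 0.56 to 0.84 at n = 50 per group, and from 0.40 to 0.60 at n = 100. Holm and Benjamini-Hochberg within families should cost less. An ethnic contrast pooled over subgroups would have up to 400 per side and go from 0.20 to 0.30.

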2.2 Trial Design & Flowchart

Proposed Methodology: In this combined cross sectional and prospective longitudinal study, non-COVID infected subjects and SARS-CoV2-positive patients of South Asian origin or White British origin diagnosed to have, or who have had, asymptomatic, mild, moderate or severe disease as per WHO or the equivalent NIH criteria will be recruited. Peripheral blood (approx 17 ml divided into 5ml clotted, 2ml EDTA, 2ml fluoride, 8ml heparinised) and stimulated whole mouth fluid (SWMF) samples (approx 4ml) will be collected from all patients and from subgroups at three further time points at approximately 2, 4 and 12 weeks. (SWMF is a combination of saliva, gingival crevicular fluid, desquamated epithelial cells, some nasopharyngeal secretions, some serum transudate). In addition to medical data available for each patient, short questionnaires on oral health and diet, a clinical examination for oral health using “PSR akaBPE” – periodontal screening and recording/basic periodontal examination of periodontal health will be undertaken. The maximum periodontal pocket depth in mm on all standing teeth using a graduated periodontal probe and the presence of bleeding on probing will be recorded for each tooth. Missing teeth will be noted.

Further information on ethnicity of South Asians will be sought, eg from Pakistan, Bangladesh, North India, South India or Sri Lankan [Sinhalese, Tamil or Muslim].

Sequence of consent, examination and samples:

Each of the two population cohorts (South Asian and White British) has four sub-groups (clinically uninfected subjects, asymptomatic/mild, symptomatic moderate/severe, and recovered). After patient information sheets and consent, then oral health questionnaires (5mins), SWMF samples (5-15 mins), oral health (periodontal) examination (10 mins), and blood via venesection (5 mins). Patients will chew on a pellet of wax until approximately 4ml SWMF is recovered by drooling into sterile universal containers (between 5 and 10 minutes normally) after which the chewed wax will be wrapped in gauze and disposed with other clinical waste in adherence to infection control procedures. Blood samples may be taken before, during or after the SWMF collection. Repeat blood and stimulated SWMF will be taken at approximately 2 weeks, 4 weeks and 12 weeks after baseline for those participants willing to take part in the sequential studies. Oral examination and partial mouth recording will not be repeated unless any material change in oral condition is evident.

Uninfected subjects will be further defined as those who do not show antibodies to nuclear capsid protein antigens. The presence of such antibodies would indicate exposure to SARS-CoV2 rather than immunisation, and would be classified as asymptomatic if no history of symptoms.

Number of samples: With South Asian and White British participants, there will be up to 100 patient samples in each of the four sub-groups (uninfected subjects, asymptomatic/mild and moderate/severe disease, and recovered.). All will be assayed for immunological parameters, and the first 50 in each group for microbiome analysis, with the remainder stored for future analysis. The first 50 participants in each group will be invited to provide sequential samples.

Times of samples: There will be repeat samples of SWMF and blood at approximately 2, 4 and 12 weeks. Those SWMF at 4 weeks will be analysed for the microbiome in addition to the immunology (see table 1).

Choice of time points: Mucosal immunological responses have a different and often shorter time frames than systemic responses. The 2 week post infection or post vaccination time point as well as the 4 week time point is to determine whether a response has been generated, and indicate possible kinetics of the mucosal response in comparison with systemic (serum) responses. The 12-week sampling point was selected as optimal to indicate longevity of any mucosal response, and any differential between a possible protective response of longer duration from a response of shorter duration.

Handling of samples: After collection, samples for GSTT haematology (Viapath) and blood glucose (if results not already available) will be sent to GSTT haematology. Study pseudoanonymised samples will be transported to the Centre for Host-Microbiome Interactions (CHMI) laboratories in Guy's Tower by the clinical research dentist. SWMF will be transported on ice. All samples will be subject to current infection control measures and containers pre-labelled. In the lab, SWMF samples will be centrifuged and immune factors including cytokines and anti-SARS-CoV2 antibodies assayed in the supernatant, whilst cellular factors determined in reconstituted pellet. DNA extraction for the microbiome studies will be performed on the saliva pellet. Peripheral blood T cell phenotypes will be assayed in the supernatant from plasma. Recruitment: Patients identified by the clinical team will be recruited by a clinical research assistant and consented. Uninfected subjects and ambulant patients will be recruited within Guys

and St Thomas' Hospital sites, from KCL sites and for General Medical Practice PIC (participant identification centre) sites. Symptomatic patients will be recruited from within outpatients or on the wards. From each subject, basic medical data will be collected and an oral health questionnaire applied, followed by SWMF, an oral examination and blood samples as above.

Timing of research: We have recognised that the success of vaccination in the UK has reduced the potential patient pool, although the Omicron strain has produced a surge in cases. Samples will be taken over 15 months and may include a greater proportion of ambulant patients than originally planned, including those identified as asymptomatic carriers from routine testing, and those to be vaccinated. Although samples will be batch analysed, we do not anticipate that robust data can be determined until towards the end of the collection period, and then compared with the data derived from the study in Chennai. Findings will be disseminated as widely as possible in academic journals, academic meetings and in appropriate form in public media and a study website.

